In addition to the weekly modules, participants will complete EMAs and EMIs 3 times per day during the Recommended Modules (i.e., first four weeks of intervention period). The EMI will be delivered concurrently with the EMA, which will collect participant’s response on their current mood, recent stressful experience, and type of stressor. Participants will then receive a list of mindfulness exercises, which will be tailored to the type of stressor/emotion they will have indicated. The intervention as well as EMAs and EMIs will be delivered on a mobile application named “Expiwell” (<https://www.expiwell.com/>).

At the end of each week, participants will also take part in a weekly “Group practice and connect” session on Zoom during the Recommended Modules (i.e., first four weeks of intervention period). The weekly sessions will be conducted in cohorts of 5-10 participants (depending on the recruitment speed), led by a research assistant who has previous experiences with mindfulness programs as well as lived experiences of early life adversity. Each session will last approximately one hour and will be structured roughly to reflect: group check-in, group discussion on past

week's weekly intervention content, one group meditation practice using audio, and reflections on the meditation practice.

- 5.3 This study will utilize Fitbit, a commercially available wearable device, for the purpose of passive data collection on sleep and physical activity. The Fitbit devices will be stored securely by the research team when not in use, distributed directly to participants during enrollment by mail, and collected at the end of the study. Names and addresses of participants will be shared with departmental operations staff through password-protected files to create shipping labels and facilitate mailing the Fitbits to participants via FedEx. When operations staff submit reconciliation for the transaction, it is on an aggregate level (i.e., without specific participant information or individual package tracking numbers). This ensures the confidentiality of each participant. Participants will be instructed on proper use and care of the device, and a pre-paid, pre-addressed return envelope will be provided so participants can directly mail the device back to the research team at the end of the study. Only authorized study team members will manage device distribution, collection, and data linkage.

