In addition to the weekly modules, participants will take part in a weekly, 1-hour "Group practice and connect" session on Zoom. The online sessions will comprise a cohort of 5-10 participants (depending on recruitment) and will be led by a research assistant, who has previous experiences with mindfulness programs as well as lived experiences of early life adversity. During each session, participants will be invited to participate in a group practice and reflection and to join group discussions on experiences regarding past week's practice. In the contact form (which is completed after the consent form), participants will be presented with the day and time of weekly sessions for the next two cohorts and asked to choose the times they are available for. If the participant is not available for either of the offered times, they will be marked as "deferred enrollment" in our participant tracking spreadsheet. A study RA will follow up with information about future cohort scheduling as that information becomes available.

Ecological momentary assessments and interventions: Over the first 4 weeks of the intervention period (i.e., Recommended Modules), participants will also complete 3 EMAs + EMIs per day through Expiwell. EMA and EMI will be delivered concurrently; the EMA will collect participant's response on their current mood, recent stressful experience, and type of stressor; participants will then receive a list of mindfulness exercises, which will be tailored to the type of stressor/emotion they will have indicated. The last EMA of the day will also include an option for the participants to submit a voice recording, serving as a "daily journal" at the end of the day to understand participant's daily experiences, including daily stressors and mindfulness practice application. To mitigate the risk of recording third-party participant voices, participants in the study will be

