11.0 Vulnerable Populations

11.1 N/A

12.0 Local Number of Subjects

12.1 We anticipate enrolling 44 *participants in the single-arm trial*.

12.2 A larger number of young adults will be screened for eligibility, and 44 participants will be recruited to enroll in the single-arm trial. From these 44 participants, we aim to have at least 35 participants (i.e., approximately 80%) who complete all intervention procedures and follow-up assessments. Screening more participants ensures that we can meet the target enrollment despite ineligible candidates, and enrolling more ensures that we collect enough data points even with potential withdrawals.

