16.2 N/A

17.0 Data Management and Confidentiality

17.1 Quantitative data will be analyzed using a combination of descriptive and inferential statistics. Feasibility and acceptability data (e.g., CSQ-8 and SEF scores, proportion of completed EMA prompts, engagement metrics such as weekly practice rates and frequency of practice use) will be summarized using means and standard deviations. Preliminary effects on other primary, secondary, and exploratory outcomes (e.g., depression, anxiety, sleep quality, emotion regulation, mindfulness) will be evaluated using repeated measures analyses, such as mixed-effects models, to characterize effect sizes (e.g., Cohen's *d*). We will use mixed-effects modeling with time as fixed effect and participant as random effect to model trajectories, incorporating baseline covariates, to account for within-subject correlations across time points. EMA data will be analyzed using mixed-effects models to assess within-person day-to-day associations between stress and intervention engagement.

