Pre-Post Changes (Clinical Outcomes) As a single-arm trial, we will use repeated measures ANOVA to assess preliminary changes in the primary clinical targets of depression (e.g., measured via PHQ-9) and anxiety (e.g., measured via GAD-7) from T1 to T2 (and T3 follow-up), characterizing within-group effect sizes using Cohen's *d*. To model individual clinical trajectories, we will use mixed-effects modeling with time entered as a fixed effect and participant as a random effect, incorporating relevant baseline covariates (e.g., age, gender, ELA severity).

EMA/Longitudinal Data Analysis

We will leverage the high-density EMA data using linear mixed-effects models to assess within-person, day-to-day, and moment-to-moment associations. Specifically, we will use time-lagged

analyses to evaluate the immediate, temporal impact of intervention engagement. For example, we will model whether the completion of an audio module at time t predicts significant reductions in momentary negative affect, anxiety, or perceived stress at the subsequent EMA prompt (time $t+1$). Additionally, we will visualize the interrelations between momentary stress, engagement with audio modules, and subsequent mood fluctuations via temporal network models.

To assess **momentary mechanisms**, we will utilize 1-1-1 Multilevel Structural Equation Modeling (MSEM). We will test whether momentary activation of specific psychological states (e.g., interoception, cognitive defusion, or acceptance/willingness) measured immediately post-EMI significantly mediates the relationship between EMI engagement at time t and reductions in negative affect at the subsequent EMA prompt (time $t+1$). We will conduct mediation analysis to understand which mechanism carries the largest indirect effect on symptom reduction. Additionally, we will visualize the interrelations between daily stressors, momentary mechanism activation, and subsequent mood fluctuations via temporal network models.

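### The clinical models ignore Zoom cohort, so standard errors for depression and anxiety change will be too small if change is correlated within cohort

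*SAP*

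**What the plan says.** Protocol 5.2 describes the group component: "The weekly sessions will be conducted in cohorts of 5-10 participants (depending on the recruitment speed), led by a research assistant". Protocol 6.2 repeats it: "The online sessions will comprise a cohort of 5-10 participants (depending on recruitment) and will be led by a research assistant". The sessions last about an hour and run weekly through the four Recommended weeks, with discussion, a group meditation and reflection. Cohorts form by availability: "participants will be presented with the day and time of weekly sessions for the next two cohorts and asked to choose". The modules and the three daily EMA/EMI prompts are delivered to each person through the app.

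For depression and anxiety, the SAP (Pre-Post Changes) specifies a repeated-measures ANOVA over T1, T2 and T3 with within-group Cohen's d, and then "mixed-effects modeling with time entered as a fixed effect and participant as a random effect". Protocol 17.1 has the same structure: "time as fixed effect and participant as random effect". The baseline covariates are given as examples (age, gender, ELA severity) and cohort is not among them. Neither document mentions a cohort or leader term, a cluster-robust variance, an ICC or a sensitivity analysis for clustering. Cohort is not named among the retained de-identified data in Protocol 7.1 and 7.2, although the participation records in 7.2 could be read to include it.

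**The concern.** A participant random effect accounts for repeated measures on one person. It does not account for change shared by people who spend four weeks in the same small group. Such sharing is plausible here: the same peers, the same discussions and the same calendar weeks. If it occurs, the effective sample size for mean change is below the head count, and both stated models understate the standard error.

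What is at stake is the stated precision of the preliminary efficacy results, which are meant to inform later studies. The point estimate of mean change is not biased by leaving cohort out.

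**Working it through.** **Plan's own figure.** Protocol 12.2 states "44 participants will be recruited to enroll in the single-arm trial" and "we aim to have at least 35 participants (i.e., approximately 80%) who complete all intervention procedures and follow-up assessments". Check: 35/0.80 = 43.75, rounded up to 44, and 35/44 = 79.5%. This reproduces. The documents give no power, alpha or precision calculation for the clinical outcomes, so there is no further figure to reproduce.

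**Number of cohorts.** 44/10 = 4.4, so at least 5 cohorts. 44/5 = 8.8, so at most 8 full cohorts.

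**Assumed inputs.** The ICC of the change score within cohort is not stated; I use 0, 0.02, 0.05 and 0.10. I assume a two-sided 5% level, near-equal cohort sizes, and between 35 and 44 analysed.

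**Design effect.** DE = 1 + ICC x (sum of squared cohort sizes / N - 1). The standard error is understated by a factor of sqrt(DE).

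- Largest case, 44 in 5 cohorts (9, 9, 9, 9, 8): the sum of squares is 4 x 81 + 64 = 388, and 388/44 - 1 = 7.82.
- Smallest case, 35 in 8 cohorts (three of 5, five of 4): the sum of squares is 75 + 80 = 155, and 155/35 - 1 = 3.43.

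**Test size.** With two time points and complete data, the repeated-measures ANOVA test of time is the square of a one-sample t on change. I therefore simulated that t test with cohort ignored. Simulation error and differences between repeat runs are about 0.2 percentage points.

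| Assumed ICC | DE, smallest to largest case | SE understated by factor | True error of nominal 5% test |
|---|---|---|---|
| 0 | 1.00 | 1.00 | 5% |
| 0.02 | 1.07-1.16 | 1.03-1.08 | about 5.8-6.9% |
| 0.05 | 1.17-1.39 | 1.08-1.18 | about 7.0-9.6% |
| 0.10 | 1.34-1.78 | 1.16-1.33 | about 8.9-14.3% |

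A t test on the cohort mean changes, with (number of cohorts - 1) degrees of freedom, held about 5% in every scenario.

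**Which model term matters.** In a small mixed-model check (40 datasets, 44 participants, 6 cohorts, ICC 0.10), the true standard error of the time effect was 0.193. The mean estimated standard error was 0.151 with participant only, 0.151 after adding a cohort intercept, and 0.198 after adding a cohort-by-time effect. A cohort intercept alone cancels out of the change contrast.

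**How well cohort variance can be estimated.** With 5-8 cohorts and a true ICC of 0.05, the moment (ANOVA) estimate of the cohort variance of change is zero or negative in about 39-43% of runs. A cohort-by-time model would then often collapse to the current one even though clustering is present.

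**Cost of the cohort-mean interval.** Ratio of t quantiles with no clustering: 2.365/2.032 = 1.16 (8 cohorts, 35 analysed) to 2.776/2.017 = 1.38 (5 cohorts, 44 analysed). It is therefore 16-38% wider from degrees of freedom alone.

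**The case against.** The case for leaving the plan alone has several sound parts.

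- The group session is one hour a week for four weeks within an app-delivered programme. That favours the lower ICCs, especially at T3, which falls 3 months after baseline and well after the sessions end. This stands.
- Both documents refer to a research assistant as leader and do not say whether leaders differ between cohorts. If one person leads all of them, leader adds no between-cohort variance. This stands.
- Choosing a slot by availability may sort people on baseline level, but a change score removes level differences. Sorting alone does not show that change is correlated. This stands.
- The SAP names no alpha or confidence interval for clinical change and calls it preliminary; the primary outcomes are benchmark proportions. This limits the impact. Both models nevertheless produce standard errors and tests that will be read.
- Without a control arm, regression to the mean and natural recovery may distort a pre-post p-value more than a design effect near 1.2. That is true, but it is a separate problem and does not remove this one.
- Cohort membership is known operationally from scheduling, so it is not irretrievably lost. That is fair; what is missing is a commitment to carry it into the analysis data.

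A reader might infer that the planned intervals are certainly too narrow, or that GEM as a whole is delivered in groups. The documents support neither: they give no ICC, and most of the content reaches participants individually. A reader might also expect this pilot to supply a usable planning ICC. With 5-8 cohorts it cannot do so with any precision.

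**Conclusion.** The omission is a fact of the text: every participant is placed in a small led group, and no stated clinical model accounts for it. The consequence is conditional. Any positive within-cohort correlation of change makes the standard errors too small: by a factor of about 1.03-1.08 at an ICC of 0.02, 1.08-1.18 at 0.05 and 1.16-1.33 at 0.10. With no correlation there is no effect. These sizes rest on assumed ICCs, near-equal cohorts and 35 to 44 analysed. If retention only just met the SAP's 70% benchmark (0.70 x 44 = 30.8, about 31), cohorts would be smaller and the inflation somewhat less.

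The point is worth correcting because it costs little and the results will feed later trials. It does not touch the feasibility and acceptability benchmarks on which the pilot is primarily judged.

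**What to change.** 1. Record cohort and session leader for each participant as variables in the de-identified analysis data.
2. Pre-specify a sensitivity analysis of T1-T2 and T1-T3 change in PHQ-9 and GAD-7: a t-interval on the cohort mean changes with (number of cohorts - 1) degrees of freedom, reported beside the current model. State that it weights cohorts equally and uses participants with both assessments.
3. Optionally, add a mixed model with a cohort-by-time random effect and Kenward-Roger or Satterthwaite degrees of freedom. A cohort intercept alone does not correct the change contrast. Because the cohort variance will often be estimated as zero, this model should not replace item 2.
4. If the cohort ICC is reported, give its interval and describe it as imprecise.

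The cost is two recorded variables and a short SAP paragraph. The statistical price is the cohort-mean interval, about 16-38% wider even when there is no clustering, which is a reason to present it as a sensitivity analysis and keep the current main model.

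### The SAP states neither a mediator value at prompts without an EMI nor adjustment for affect at t, so the momentary indirect effect may be inestimable and the lagged effects confounded

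*SAP*

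**What the plan says.** Under EMA/Longitudinal Data Analysis the SAP describes two kinds of model.

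- **Lagged mixed models.** The example asks whether completing an audio module at t "predicts significant reductions in momentary negative affect, anxiety, or perceived stress at the subsequent EMA prompt".
- **A 1-1-1 multilevel structural equation model.** It asks whether a state such as interoception, defusion or acceptance, "measured immediately post-EMI significantly mediates the relationship between EMI engagement at time t and reductions in negative affect" at the next prompt, carries the effect of the EMI.

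Neither description names affect or stress at t as a covariate, a centring rule, or a treatment of lags that cross the night. Baseline covariates are named only for the T1 to T3 trajectory model.

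Protocol 6.2 delivers the EMI together with every EMA, three times a day for four weeks. The EMA records the participant's "response on their current mood, recent stressful experience, and type of stressor", and the exercise list is then "tailored to the type of stressor/emotion they will have indicated". Protocol 6.4 describes EMA content as stress, mood and emotional states, and says the app logs frequency and duration of both EMI-prompted and self-initiated practice. Items on interoceptive awareness, de-centering and perseverative thinking appear in the weekly survey.

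**The concern.** Two gaps matter, and they are separate.

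**The mediator's comparison.** A mediation model needs the mediator both when the exposure is present and when it is absent. A state defined as measured after the EMI may have no value when the participant declines the exercise, and no document says what happens then.

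**Confounding by the state at t.** Nothing is randomised at the prompt level. The participant reports mood and stressor, sees a list built from that report, and decides whether to practise. If the decision depends on how the participant feels, engaged and non-engaged prompts start from different affect. Affect tends to drift back towards the person's own mean by t+1 whether or not the exercise works. Protocol 17.1 itself plans to study the within-person association between stress and engagement, so the plan treats such dependence as a live possibility.

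Mechanism through real-time data is the secondary objective, and the exploratory results are meant to inform later studies. Model terms can be added afterwards. Mechanism items that were never asked cannot.

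**Working it through.** The plan gives no power, effect size or precision figure for these analyses, so there is none to reproduce.

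**1. Identification of the engagement-to-mediator path.** Let X = 1 if an exercise is done and 0 if not, and suppose the mediator M exists only when X = 1. On all rows with M observed, the intercept column and X are identical, so the design [1, X] has rank 1 where 2 is needed. The slope of M on X is undefined, and so is the indirect effect, which is a product containing it. Practice duration could replace X, but only users would have M, so it gives a dose gradient among users and no contrast with non-use.

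**2. Direction of confounding.** Let φ be the lag-1 autocorrelation of affect and δ the excess negative affect at engaged prompts. With no true effect:

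- change from t to t+1, engaged minus not engaged: -(1-φ)δ
- level at t+1, engaged minus not engaged: φδ

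The documents give neither φ nor δ. Assuming φ 0.3 to 0.5 and δ 0.3 to 0.7 SD, the change score runs from -(0.5 × 0.3) = -0.15 to -(0.7 × 0.7) = -0.49 SD. The level runs from 0.3 × 0.3 = +0.09 to 0.5 × 0.7 = +0.35 SD. If people skip practice when distressed, δ is negative and both signs reverse.

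**3. Simulation at the planned size.** From the protocol: 44 people and 3 × 28 = 84 prompts each, 3,696 in all. Assumed: first-order autoregressive affect, baseline uptake about 40%, and log-odds of use rising by 0.5 or 1.0 per SD of affect at t. Each cell had 100 replicates, and all models used person-mean-centred variables and cluster-robust standard errors. The true effect is zero, and entries are mean estimates in within-person SD:

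| Autocorrelation | Selection (log-odds per SD) | Change, unadjusted | Level, unadjusted | Level, adjusted for affect at t |
|---|---|---|---|---|
| 0.2 | 0.5 | -0.386 | +0.086 | -0.002 |
| 0.2 | 1.0 | -0.673 | +0.154 | +0.001 |
| 0.4 | 0.5 | -0.286 | +0.178 | 0.000 |
| 0.4 | 1.0 | -0.498 | +0.310 | +0.002 |
| 0.6 | 0.5 | -0.194 | +0.264 | -0.001 |
| 0.6 | 1.0 | -0.335 | +0.469 | +0.001 |

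The false-positive rate was 100% for change, 72 to 100% for level, and 5 to 9% after adjustment. With no selection on affect, all three estimates were near zero.

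The formulas agree with the table. In the row 0.4 / 0.5, δ = 0.178 + 0.286 = 0.464. The formulas then give a level of 0.4 × 0.464 = 0.186 and a change of -0.6 × 0.464 = -0.278, each within 0.01 of the simulated value.

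With a true effect of -0.20 (autocorrelation 0.4, selection 0.5), change gave -0.49, level -0.02 and adjusted -0.20.

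**4. What adjustment does not remove.** With measurement-error SD 0.5 and selection on true affect, the adjusted model kept a bias of +0.01 to +0.11 SD, towards harm. Its false-positive rate ran from 6% to 90%, highest at autocorrelation 0.6 and selection 1.0.

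**5. Overnight lags.** At 3 prompts a day there are 84 - 1 = 83 consecutive pairs, 56 within a day and 27 overnight: 27/83 = 33%. At 4 a day there are 112 - 1 = 111 pairs, 27 of them overnight: 27/111 = 24%.

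**The case against.** Several stronger readings are tempting, and the documents do not support them.

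- **That stress triggers the EMI.** It does not. The EMI comes with every EMA, and the report only shapes the list. Where Protocol 6.2 separates EMI-triggered from self-initiated practice, the EMI is what prompts the practice. Stress-driven uptake is plausible but assumed.
- **That the mediator exists only after a completed exercise, or is not collected at all.** Since an EMI accompanies every prompt, post-EMI could mean after every offer. The SAP says these states are measured, and the protocol refers to a measures file that is not among the documents. What can be said is that neither the protocol nor the SAP states the rule.
- **That the analysis will credit regression to the mean to the app.** That follows only from an unadjusted change score. The SAP speaks of "reductions in negative affect at the subsequent EMA prompt", which suggests change but does not define it. An unadjusted level errs the other way.
- **That none of the EMA models can work.** The rank problem belongs to the mediation model. The SAP's lagged example uses audio modules, which are weekly content and not a response to a momentary report. The missing adjustment still matters there if people choose when to listen according to how they feel, but the sizes above were worked out for the EMI.
- **That a third of lags cross the night.** This is true at three prompts a day, but the SAP's exit-interview paragraph and the protocol's inclusion criteria allow three to four.

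It is also fair to say that this is a single-arm feasibility study with exploratory efficacy analyses, and that weekly mechanism items offer a slower view of the same processes. That lowers the severity. It does not supply the missing momentary comparison or the missing covariates.

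**Conclusion.** The concern holds as a gap in specification. If the items follow only completed exercises, the indirect effect cannot be estimated from yes/no engagement. This is a matter of algebra and needs no numerical assumption beyond that reading. If use depends on current affect, the unadjusted lagged effect is biased: by -0.19 to -0.67 SD for a change score and +0.09 to +0.47 SD for a level, against about zero after adjustment. Those sizes rest on assumed autocorrelation (0.2 to 0.6), selection (0.5 to 1.0 log-odds per SD) and uptake, and on affect measured without error. The severity is moderate, not must-fix. Calculation of the primary feasibility and acceptability benchmarks does not depend on these models.

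**What to change.** 1. **Mediator and exposure.** Ask the mechanism items at the end of every prompt, whether or not an exercise was done, and define engagement as done versus declined. Settle this before the first cohort starts. Each item adds at most 84 responses per person at three prompts a day, so three items add at most 252. That burden bears on the EMA adherence benchmark, so keep the items few. If they already follow every offer, a sentence in the SAP is enough.
2. **Model.** In the lagged models, regress affect at t+1 on person-mean-centred engagement at t, adjusting for affect and stressor at t, time of day and study day. Put the same adjustment in both MSEM equations, mediator on engagement and affect at t+1 on mediator and engagement, with the paths of interest at the within-person level. The EMA already collects the affect and stressor data, so this costs only SAP wording.
3. **Overnight pairs.** Give them their own coefficient, or a sensitivity analysis without them. Dropping them from the main analysis is optional and would cost 27 pairs per person.
4. **Reporting.** Describe the results as associations and soften the wording on impact. Measurement error can leave bias after adjustment, and self-initiated practice can occur after a declined prompt.
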